### 649 6.2 Blood samples

650 Glycaemic control is evaluated by an OGTT and level of HbA1c on the day of inklusion (basal level) 651 and after 16 weeks of treatment. The endocrine pancreas function is assessed by plasma 652 concentrations of insulin, C-peptide and plasma glucagon. Additionally levels of incretin hormones 653 will be evaluated in the fasting state and after oral glucose (amount of blood max 150 ml. per test)

ASSESSMENT OF SAFETY
ASSESSMENT OF SAFET

### 657 **7.1 Serious adverse event (SAE) and serious adverse reactions (SAR)**

658 **7.1.1 Definition of SAE and SAR** 

SAE, i.e. there exists a relationship between the drug or the experiment and the untoward effect, and
 SAR, i.e. a noxious event occurring in a treated patient in an experiment, which is not necessarily related to
 the treatment is any untoward medical occurrence that at any dose:

- 662 1) results in death or
- 663 2) is life-threatening or

664

NOTE: The term "life-threatening" in the definition of "serious" refers to an event in which the patient was at risk of death at the time of the event; it does not refer to an event, which hypothetically might have caused death if it were more severe.

#### 668

- 669 3) requires inpatient hospitalization or prolongation of existing hospitalization or
- 4 results in persistent or significant disability/incapacity, or
- 671 5) is a congenital anomaly/birth defect
- 672
- 673 and is either known (SAE or suspected (SAR)
- 674

In addition, medical and scientific judgment is required to decide if prompt notification is required in other situations, i.e. any event which the investigator regards as serious that did not strictly meet the criteria above but may have jeopardized the subject or required intervention to prevent one of the outcomes listed above, or which would suggest any significant hazard, contraindication, side effect or precaution that may be associated with the use of the drug.

### 680 Reporting of SAE and SAR

681 The investigators must immediately report any SAE and SAR to the sponsor occurring between the 682 treatment with study drug and completion of last follow-up, i.e., 1 month after the treatment, whether or

<sup>1 Complications occurring during hospitalisation are AEs and are SAEs if they cause prolongation of the current hospitalisation. Hospitalisation for elective treatment of a pre-existing non worsening condition is not, however, considered an AE. The details of such hospitalisations must be recorded on the medical history/physical examination page of the CRF.

 $^{2}$  An AE is incapacitating or disabling if it results in a substantial and/or permanent disruption of the patient's ability to carry out normal life functions.

not considered related to study drug. All pregnancies occurring during the study, although not SAEs, should
 be reported using the SAE reporting procedures and will be reported directly to Novo Nordisk.

685

The investigator should not wait to receive additional information to fully document the event before notifying a SAE, although additional information may be requested. Where applicable, information from relevant laboratory results, hospital records and autopsy reports should be obtained. The investigators are also required to submit follow-up reports until such time as the SAE or SUSAR has resolved or in the case of permanent impairment, until the SAE or SUSAR stabilizes.

691

692 The sponsor will report all SAEs to the Ethics Committees (IECs) and all SARs to the Danish Medical Agency 693 once a year together with a report on the safety of the study patients. All SAEs and SARs will be reported to 694 Novo Nordisk within 15 days from the investigator getting knowledge of the case. Details of SAEs and SARs 695 will be noted on the adverse event pages in the CRF. There will be no formal follow-up after last patient 696 visit but all patients have the opportunity to contact the investigators in case of uncertainties. Instances of 697 death, congenital abnormality or an event that is of such clinical concern as to influence the overall 698 assessment of safety, if brought to the attention of the investigators at any time after cessation of study 699 medication and linked by the investigators to this study should be reported.

700

### 701 **7.1.3** Suspected unexpected serious adverse reaction (SUSAR)

702 Any serious adverse event that is unexpected will immediately be reported by sponsor to the Danish 703 Medical Agency. SUSARs that result in death or are life-threatening will be reported to the Danish Medical 704 Agency at the latest 7 days after the sponsor has been notified about it. After reporting the SUSAR, the 705 sponsor will provide the Danish Medical Agency all relevant further information on the course of case 706 within 8 days. SUSARs that do not result in death or are not life-threatening will be reported to the Danish 707 Medical Agency at the latest 15 days after sponsor has been notified about the SUSAR. Any report will be 708 followed by comments about any consequences for the research project. Sponsor will moreover report any 709 SUSARs to the marketing authorization holder (Novo Nordisk).

710

### 711 7.2 Adverse event

### 712 **7.2.1 Definition of adverse event**

An adverse event (AE) is any untoward medical occurrence in a patient or clinical investigation subject administered a pharmaceutical product and which does not necessarily have a causal relationship with this treatment. An AE can therefore be any unfavourable and unintended sign (including an abnormal laboratory finding), symptom, or disease temporally associated with the use of a medicinal (investigational) product, whether or not related to the medicinal (investigational) product. All events occurring after the subject has signed the study consent form should be reported as an adverse event.

### 719 **7.2.2 Reporting of adverse event**

AEs related to the treatment according to the investigator will be recorded in the CRF. All reported AE's will be followed up until resolved or as clinically required.

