### 722 **7.2.3** Assessment of adverse event

AEs may be reported spontaneously by the patient through open (non-leading) questioning during the study. As far as possible, all AEs must be described by their duration (start and stop date), severity (mild, moderate, or severe), relationship to treatment (yes, uncertain, no), and according to the need of other specific therapy. The onset of AEs will be classified relative to the stage of treatment.

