### 727 **7.3 Reporting at the end of the study**

All SAEs, SARs, SUSARs, and AEs will be reported to the Danish Medical Agency at the end of the study.

729

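### Protocol 7.2.2 ties CRF recording of adverse events to the investigator's judgement of relatedness, contradicting 7.2.1, 7.2.3 and 7.3 and putting non-serious events judged unrelated at risk of being lost

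*Supplement*

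**What the plan says.** The rule for entering adverse events in the CRF is one sentence in protocol section 7.2.2: "AEs related to the treatment according to the investigator will be recorded in the CRF".

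The neighbouring sections are wider:

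- Section 7.2.1 defines an AE as an untoward occurrence "whether or not related to the medicinal (investigational) product" and adds: "All events occurring after the subject has signed the study consent form should be reported as an adverse event".
- Section 7.2.3 asks that all AEs be described as far as possible, including by "relationship to treatment (yes, uncertain, no").
- Section 7.3 states: "All SAEs, SARs, SUSARs, and AEs will be reported to the Danish Medical Agency at the end of the study".

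Serious events have their own rule. Under Reporting of SAE and SAR, the investigator reports any of them whether or not it is thought related to the drug, and "Details of SAEs and SARs" are entered on the adverse event pages of the CRF. The reporting period lies between "treatment with study drug and completion of last follow-up, i.e., 1 month after the treatment". The same section also says: "There will be no formal follow-up after last patient" visit.

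The final SAP (Procedure) runs the safety analyses on everyone randomised who took at least one dose. It does not say which AEs are counted.

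**The concern.** Randomisation protects a comparison of all events by arm. It does not protect a comparison of events that have first passed through an opinion about cause. If sites worked to 7.2.2, two things could follow for non-serious AEs.

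First, events would be under-counted. Those most easily lost are the ones nobody expects of the drug. This matters here because section 4.1 says that daily injections of this kind had not, to the authors' knowledge, been tried in psychiatric patients, so there is little experience to guide attribution.

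Second, attribution could differ between arms. Section 1.2 expects gastrointestinal symptoms and possibly weight loss on liraglutide. An investigator who sees these might guess the allocation and attribute other complaints accordingly. Events that were never recorded cannot be recovered at the analysis stage.

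**Working it through.** **Step 1: set the sections side by side for one event.** Take a non-serious AE that the investigator judges unrelated.

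- 7.2.1: it is an AE and is to be reported.
- 7.2.3: it is described and graded *no* for relationship.
- 7.3: it goes to the authority at the end of the study.
- 9.3: as study data, it belongs in the patient's CRF.
- 7.2.2: it is not among the events to be recorded in the CRF.

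A site cannot act on 7.2.2 in its natural reading and on the other four together. An event graded *uncertain* has no clear place either.

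**Step 2: repeat for a serious event.** It is reported and entered in the CRF whatever its attribution. The explanations of SAE and SAR in 7.1.1 appear interchanged, but both kinds go in the CRF, so this exception holds either way. The gap is confined to non-serious AEs.

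**Step 3: look for a repair elsewhere.** Section 5.2 has AEs noted throughout treatment but does not say where. Table 1 has no AE row. The SAP lists side effects and serious adverse events among its subgroup and sensitivity variables without defining them. The table of protocol changes names no amendment to AE recording. The full text of versions 1.3 to 3.2 is not shown.

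**Step 4: size, by illustration.** The plan gives no AE rate and no attribution rate, so there is no figure of its own to reproduce on this point. The only design figure used is 48 per group. It reproduces from the SAP's inputs (means 1695 and 1800, SD 158, two-sided 5%, power 90%):

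n = 2 × (1.960 + 1.282)² × 158² / 105² = 47.6, so 48 per group and 96 in total.

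This number is unaffected by the point.

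Now assume true rates p1 = 30% and p0 = 10%, and let a share c of events be judged related, equal in both arms. The recorded rates are c × p1 and c × p0. With d the recorded difference and p̄ the mean of the two recorded rates r1 and r0,

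power = Φ{ [d − 1.96 √(2p̄(1 − p̄)/48)] / √([r1(1 − r1) + r0(1 − r0)]/48) }.

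| Share recorded, both arms | Recorded rates | Risk difference | Risk ratio | Power |
|---|---|---|---|---|
| 100% | 30% vs 10% | 20 points | 3.0 | 69% |
| 75% | 22.5% vs 7.5% | 15 points | 3.0 | 54% |
| 50% | 15% vs 5% | 10 points | 3.0 | 37% |
| 25% | 7.5% vs 2.5% | 5 points | 3.0 | 20% |

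**Step 5: unequal attribution, also assumed.** Let there be no true difference.

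- True rate 20% in both arms, 80% recorded on liraglutide and 50% on placebo: 0.20 × 0.80 = 16% against 0.20 × 0.50 = 10%, a risk ratio of 1.6.
- True rate 30% in both arms, 60% and 30% recorded: 0.30 × 0.60 = 18% against 0.30 × 0.30 = 9%, a risk ratio of 2.0.
- Equal shares recorded: the ratio stays at 1.0.

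**The case against.** The best defence is that 7.2.2 does not contain the word *only*. It says that related AEs are recorded and does not say that others are left out. Sections 7.2.1, 7.2.3, 7.3 and 9.3 all point to full capture, and sites may have followed them. This stands as far as practice goes: the documents show conflicting instructions, not which one was obeyed. It does not rescue the wording, because a rule that singles out related events has no purpose unless the others are treated differently.

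A reader might go further and infer that the relationship grade *no* can never be used, that an unsuspected harm would be recorded as zero, or that psychiatric worsening is hidden. The documents do not support this. Unrelated serious events are entered and can be graded *no*. Hospitalisation makes an event serious (7.1.1). Marked worsening on the CGI-I, or a change of more than 20% in the olanzapine or clozapine dose, is a withdrawal reason recorded in the CRF (4.5). The CGI scales, function and quality of life are scheduled at week 16 (Table 1). These sources do not replace an AE listing, but they limit what can be lost.

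A reader might also infer that the safety comparison is biased as a matter of fact. The trial is double-blind and the assisting nurses are blinded too. With equal attribution the risk ratio is preserved, as Step 4 shows. The unequal shares in Step 5 are assumptions with no basis in the documents.

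The follow-up window is a lesser matter. A one-month duty to report SAEs can coexist with no scheduled visit after the last one. Table 1 ends at week 16, but it belongs to version 1.2. Version 2.0 added a 1-year follow-up whose text is not shown, so whether any mismatch remained cannot be judged.

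**Conclusion.** The contradiction is real, and nothing shown resolves it. It concerns non-serious AEs judged unrelated, and perhaps those judged uncertain. Serious events, the primary endpoint and the sample size are not affected.

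If sites followed 7.2.2, the firm consequence is under-counting: absolute differences between arms shrink in proportion to the share recorded, and power falls with them. The sizes given rest on assumed event and attribution rates. A distorted risk ratio is a possibility that depends on attribution differing by arm. Whether any loss took place depends on site practice, which the documents do not show.

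**What to change.** 1. Reword 7.2.2 so that every AE from consent onward is recorded in the CRF irrespective of causality, with causality kept as a data field on the 7.2.3 scale.
2. State in the SAP that the safety tables count all-cause AEs by arm, with related AEs shown as a subset.
3. The SAP describes the data set as locked, so also state which rule the sites followed. If only related non-serious AEs were collected, say so in the report and present the AE tables as such.
4. As a secondary clarification, reconcile the 1-month SAE period with the sentence on no formal follow-up, and say how events in that period are to be learned of.

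The cost is a change of wording in the protocol, CRF and SAP, and somewhat more data entry at visits already held. For data already collected, it is one or two sentences in the report.

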#### 71 Procedure

All analyses will be carried out with the treatment groups still blinded and labeled as "treatment group A" and "treatment group B". Before dividing participants into group A and group B, the statistical plan was completed and uploaded on clinicaltrials.gov, and the data set was locked. The final unblinding of treatment groups (liraglutide or liraglutide placebo), will not be carried out until all statistical analyses are performed. All analyses will be performed using SAS 9.4, with  $\alpha$  set at 0.05 and two-sided testing.

All efficacy analyses will be performed using a modified intention-to-treat principle. All participants who were randomized, received at least one dose of the trial compound (liraglutide or liraglutide placebo) and who had at least one assessment after baseline will be included in the efficacy analyses. All safety analyses will be performed in the intent-to-treat sample that includes all participants, who were randomized and received at least one dose of the trial compound (liraglutide or liraglutide placebo).

84

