### **5.2 Treatment evaluation**

A 75 g-oral glucose tolerance test (OGTT) will be performed at baseline and after 16 weeks of treatment in all participants. The procedures are as follows: 75 g water-free glucose dissolved in 300 ml H2O is to be ingested during the first 5 minutes of the test. Blood is sampled from a cannula inserted in a cubital vein 15, 10 and 0 min before oral intake of the glucose load and 5, 10, 15, 20, 30, 40, 50, 60, 90, 120, 150, 180 and 240 min after. At each time-point blood is drawn for serum / plasma analyses for glucose, insulin, C-peptide, glucagon, intact and total GLP-1 and GIP, respectively. During both experimental days the hand with the cannula is kept in a heating box (42  $^{\circ}$ C) throughout the test.

After baseline examinations the groups will be randomized to receive blinded treatment with either liraglutide s.c. using Liraglutide 6.0 mg/mL, 3.0 mL pre-filled pen-injectors or placebo, using Liraglutide placebo, 3.0 mL pre-filled pen-injectors.

627 Victoza®/Liraglutide placebo, 3.0 mL pre-filled pen-injector is administered subcutaneously one time 628 daily in the entire treatment period (Day 1-7: 0.6 mg Victoza®/Liraglutide placebo, 3.0 mL pre-filled pen-629 injector; Day 8-14: 1.2 mg Victoza/Liraglutide placebo, 3.0 mL pre-filled pen-injector; Day 15 and rest of the 630 study: 1.8 mg Victoza®/Liraglutide placebo, 3.0 mL pre-filled pen-injector). Patients who, due to adverse 631 events, do not tolerate up-titration to 1.8 mg Liraglutide 6.0 mg/mL, 3.0 mL pre-filled pen-injector will remain on 1.2 mg of Liraglutide 6.0 mg/mL, 3.0 mL pre-filled pen-injector. The patients are instructed in 632 633 injection technique. Compliance and adverse events are noted during the entire period. If the patient 634 cannot self inject Victoza®/Liraglutide placebo, 3.0 mL pre-filled pen-injector, a contact person will assist. 635 Assisting contact persons, i.e. assisting nurses, are blinded to the treatment too.

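### Section 7.2.2 ties CRF entry of adverse events to the investigator's attribution, contradicting 7.2.1, 7.2.3, 7.3 and 9.3, so non-serious events judged unrelated may be lost

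*Supplement*

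**What the plan says.** The rule on CRF entry is in protocol section 7.2.2: "AEs related to the treatment according to the investigator will be recorded in the CRF". The section adds that reported events are followed up, but says nothing about recording events judged unrelated.

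Other sections bear on the same question:

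- **7.2.1** defines an adverse event "whether or not related to the medicinal (investigational) product" and adds: "All events occurring after the subject has signed the study consent form should be reported as an adverse event".
- **7.2.3** asks that all adverse events, as far as possible, be described by several attributes, among them "relationship to treatment (yes, uncertain, no").
- **5.2** states: "Compliance and adverse events are noted during the entire period".
- **7.3** states: "All SAEs, SARs, SUSARs, and AEs will be reported to the Danish Medical Agency at the end of the study".
- **9.3** has all data obtained in the study documented in the individual CRF.
- **Reporting of SAE and SAR** (under 7.1) requires serious events to go to the sponsor even when "not considered related to study drug", with details on the CRF's adverse event pages.

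The final SAP, under Procedure, states: "All safety analyses will be performed in the intent-to-treat sample that includes all participants" who were randomised and dosed. It does not say which adverse events are tabulated or how the arms are compared. Under Subgroup and sensitivity analyses it lists side effects as a variable.

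**The concern.** In a randomised trial, the comparison of adverse events between arms does not depend on anyone's opinion about cause, provided that all events are counted. If an event enters the data only when the investigator thinks the drug caused it, that opinion is back in the comparison.

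This matters in this population. Psychiatric worsening, sedation, and metabolic or cardiovascular symptoms are readily attributed to the illness or to clozapine or olanzapine. For such events individual attribution is least reliable, and the comparison with placebo is most useful.

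There is a second, weaker route to harm. Sections 1.2 and 10.3 name gastrointestinal symptoms as the main or common effects of the drug. A participant with such symptoms may be taken to be on liraglutide, and that participant's other events may then be called related more often. The filter could therefore work unequally between arms despite blinding.

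**Working it through.** No stated figure underlies the rule, so the main check is a comparison of the texts.

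**Can the sections be followed together?** Take a non-serious event after consent that the investigator judges unrelated.

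| Section | What happens to the event |
|---|---|
| 7.2.1 | reported as an adverse event |
| 7.2.3 | described, with relationship graded as none |
| 5.2 | noted |
| 7.2.2 | no provision for CRF entry; entry is stated only for related events |
| 9.3 | in the CRF, as data obtained in the study |
| 7.3 | reported to the agency at the end of the study |

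If 7.2.2 is restrictive, it conflicts with 9.3, the lowest relationship grade in 7.2.3 has no use in the CRF, and 7.3 has no CRF record to draw on for these events. If it is not restrictive, its qualifier about relatedness has no purpose. Events graded uncertain are unclear under either reading. Two sites could record differently and both claim to follow the protocol.

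**How far does it reach?** Serious events fall outside the filter, because they are reported and noted in the CRF regardless of relatedness. Safety blood samples are taken throughout (Protocol summary). Weight, blood pressure and waist are measured every 4 weeks, and the CGI scales and GAF at weeks 0 and 16 (Table 1). Withdrawal reasons go in the CRF (4.5). What remains exposed is non-serious adverse events.

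**Do later documents settle it?** Protocol version 1.2 is the only one shown in full. The table of amendments mentions no change to adverse event recording. The SAP sets the safety population only.

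**Illustration of size, on assumed rates.** Only the 48 per arm comes from the documents (SAP, Power calculation). True rates and the share judged related are assumptions. Recorded rate = true rate × share judged related. The test is Fisher's exact, two-sided 5%, with its rejection probability found by enumerating two binomials of size 48.

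*(a) True excess 30% vs 10%, same share judged related in both arms*

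| Share judged related | Recorded rates | Power |
|---|---|---|
| all recorded | 30% vs 10% | 61% |
| 50% | 15% vs 5% | 23% |
| 20% | 6% vs 2% (48 × 0.06 = 2.9 vs 48 × 0.02 = 1.0 participants) | 3% |

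*(b) No true difference, 30% in both arms*

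| Shares judged related | Recorded rates | False difference found |
|---|---|---|
| all recorded | 30% vs 30% | 3% |
| equal shares | equal | about 2–3% |
| 70% vs 50% | 21% vs 15% | 7% |
| 80% vs 40% | 24% vs 12% | 24% |

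A normal-approximation check gives the same pattern as (a). For 25% vs 5%, power is 79% with all events recorded, 65% at a share of 75%, 46% at 50% and 25% at 25%. For 30% vs 10% the values are 69%, 54%, 37% and 20%. They are higher than in (a) because Fisher's test is conservative at this size.

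Equal filtering costs events and power but creates no false difference. A false difference needs attribution to differ by arm.

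**The case against.** The strongest reply is that 7.2.2 does not contain the word only. It says that related events will be recorded, not that others will not be. Sections 5.2, 7.2.1, 7.2.3, 7.3 and 9.3 all point to recording everything, so the intention may be full capture with one badly worded sentence. This stands in part: the documents show an unresolved contradiction, not a settled rule to exclude. It does not remove the problem, because 7.2.2 is the section that tells the site which adverse events to enter.

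A reader might infer that the trial cannot show unexpected or misattributed harm. The documents do not support that. Serious events are captured whatever the attribution, 7.1.3 handles unexpected serious events separately, and laboratory and scheduled clinical measures are taken without regard to cause.

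A reader might also infer that the CRF is the only source of safety data, or that a planned between-arm test of adverse events is biased. Neither is stated. The SAP specifies no such comparison.

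Finally, the trial is double-blind, and 48 per arm was chosen for glucose AUC, not for adverse events. Even with full recording, scenario (a) reaches only 61%. The 24% in scenario (b) needs strongly unequal attribution, which nothing in the documents quantifies. These points stand and limit the claim about size.

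**Conclusion.** The contradiction is real, and as far as the documents show it is not mended later. Followed literally, 7.2.2 leaves non-serious adverse events judged unrelated out of the CRF. The likely harm is mainly loss of such events, and with it weaker ability to see non-serious harm that is easily blamed on the illness or on the antipsychotic. Distortion between arms is possible if recognisable side effects make attribution unequal. The side-effects variable in the SAP's subgroup and sensitivity analyses would carry the same gap.

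The extent cannot be derived from the documents, which give neither non-serious event rates nor shares judged related. The power and false-difference figures illustrate the mechanism on assumed values and do not estimate what happened in this trial. Because the problem is confined to non-serious events and does not touch the glucose endpoint, it is an inconsistency that should be fixed, not a flaw that invalidates the trial.

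**What to change.** Reword 7.2.2 so that all adverse events from signed consent to the end of adverse event follow-up are recorded in the CRF whatever the judged relationship, with relationship (yes, uncertain or no), severity and start and stop dates as separate fields. That brings it into line with 7.2.1, 7.2.3, 7.3 and 9.3.

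Add to the SAP that the main safety tables show all-cause adverse events by arm in the safety population, with the related subset as a secondary table, and define the side-effects variable by reference to one of these.

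The cost is protocol and SAP wording, plus somewhat more CRF entry at the 4-weekly visits where side effects are already evaluated (5.1). No new procedure and no extra participants are needed. For events noted but not entered, the source notes should be checked before the safety tables are made. An event that was written down nowhere cannot be recovered.
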